### 9.2.4 Patient Eligibility

Women will be screened for eligibility criteria for each pregnancy, should they contribute more than one pregnancy in the Registry. Any within-patient pregnancy correlations will be accommodated in the analysis as part of the statistical analysis plan (SAP).

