#### 9.2.4.2 Exclusion Criteria

- Women currently participating in another investigational device or investigational drug study, currently taking an investigational medicinal product, or having taken an investigational product within 3 months prior to LMP or during pregnancy. Other investigational procedures while participating in this study are excluded.
- Women exposed to any medication in the same pharmacological class as erenumab-aooe (ie, CGRP mAb) in the period from 5 half-lives prior to LMP through the end of pregnancy

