### **At Delivery (estimated within 4 weeks of delivery date)**

- Reporter of information (eg, patient, PCP, OB, neurologist [indication specialist], nurse midwife, infant HCP, other)
- Pregnancy outcome (eg, live birth, stillbirth, spontaneous abortion, elective or therapeutic termination)
- Reason for elective or therapeutic termination (eg, prenatal testing finding, risk to mother's health, undesired pregnancy), if applicable
- Autopsy results and pathology reports, if available
- Mode of birth (vaginal delivery, assisted delivery/cesarean section, type of anesthesia)
- Number of migraines since last follow-up; number of migraines requiring treatment, and any prescription migraine treatments
- Changes in comorbid conditions

- Erenumab-aooe treatment (including start and stop dates, dose, dosing frequency, reason for discontinuation [if applicable])
- Current medications, including start and stop dates (eg, any other OTC migraine treatment(s), folic acid and other vitamins, herbal remedies or supplements, vaccinations, or other medications used to treat chronic conditions or comorbidities)
- Changes in lifestyle risk factors (eg, smoking, caffeine consumption, alcohol use, illicit drug use)
- Patient AEs and SAEs (including event, start date, ongoing or end date, seriousness, severity, relationship to erenumab-aooe, outcome, action taken)
- Infant characteristics:
  - Gestational age at birth
  - Sex
  - Birth weight
  - Length
  - Head circumference
  - Birth order (for multiple births), and number of fetuses
  - Apgar scores (1, 5, and 10 minutes)
  - Congenital malformations noted (including description and attribution)
  - Vaccination information
  - Whether infant is breastfed
  - Infant medication(s)
  - Infant AEs and SAEs (including event, start date, ongoing or end date, seriousness, severity, relationship to erenumab-aooe, outcome, action taken)

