#### **9.3.2.2.3.3 Low Birth Weight**

An infant with low birth weight will be classified as weighing under 2500 g ([www.cdc.gov](http://www.cdc.gov)). Low birth weight can be subclassified into very low birth weight (< 1500 g) and moderate low birth weight (1500 g to 2499 g).

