#### 9.7.2.4 Analysis of the Primary and Secondary Endpoints

The prevalence of major and minor congenital malformations will be calculated using MACDP convention. Major malformations will be analyzed separately from minor malformations, with the primary analysis including only adjudicated major congenital malformations. The total prevalence will be calculated by dividing the number of adjudicated cases of each event (observed in live births, fetal deaths, elective or therapeutic terminations, and at any gestational age) by the total number of pregnancies (excluding spontaneous terminations and ectopic or molar pregnancies). The prevalence at birth will be calculated as number of cases observed in live births and stillbirths divided by the total number of births (stillbirths + live births). Data analysis for major congenital malformations will be based on first trimester exposure to erenumab-aooe.

The prevalence of pregnancy complications, including preeclampsia, pregnancy-induced hypertension, gestational diabetes, placenta previa, and preterm labor, will be summarized by dividing the number of each event by the total number of pregnant women.

The prevalence of spontaneous abortions will be calculated by dividing the number of fetal losses occurring before 20 weeks gestation by the total number of pregnancies.

The prevalence of elective and therapeutic abortion will be estimated similarly as separate outcomes.

Prevalence of preterm birth will be calculated by dividing the number of cases by the total number of births (stillbirths + live births). The prevalence of small-for-gestational-age will be calculated by dividing the number of cases by the total number of live births.

For growth and developmental delays, the prevalence will be calculated as the number of cases divided by the total number of live births.

Prevalence of primary and secondary outcome measures will be presented with 95% CIs for binomial proportion. The analyses summarized in this section will be performed on the erenumab-aooe exposed cohort and the internal comparator cohort consisting of pregnant women with migraine who were not exposed to erenumab-aooe; Characteristics can be matched or stratified in relation to the exposed cohort to control for important covariates such as maternal age (see [Section 9.7.2.5.1](#)).

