## **9.7.2.5 Comparative Analysis**

### **9.7.2.5.1 Internal Comparator Analysis**

Primary and secondary outcome frequencies in the erenumab-aooe exposed cohort will be compared with the internal comparator cohort using the risk ratio (95% CIs). Also, comparisons may be explored using ORs adjusted to relevant covariates as applicable, if a sufficient number of outcomes are available in the subgroups. The covariates of interest may include the maternal age, prior history of elective or therapeutic pregnancy termination status, other migraine treatment exposures (such as preventive migraine treatments other than erenumab-aooe), migraine type, and baseline alcohol status. In

addition, erenumab-aooe exposure specific covariates such as any preconception CGRP mAb exposure (> 5 half-lives prior to LMP) and cumulative duration of exposure to migraine therapies during pregnancy may be explored.

Additionally, to assess the impact of exposure on the primary outcomes the propensity score matching may be explored. Baseline characteristics such as age, migraine history (eg, type of migraine), migraine severity (eg, frequency, duration, treatment burden) and parameters of obstetric history will be explored to match between the erenumab-aooe exposed and internal comparator cohorts.

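### Binomial intervals on births treat co-twins as independent, so the preterm-birth interval (and low birth weight, if counted per infant) is too narrow; plurality is recorded but named in no analysis

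*Protocol*

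**What the plan says.** Section 9.7.2.4 of the protocol sets the unit of analysis outcome by outcome:

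- Preterm birth: "Prevalence of preterm birth will be calculated by dividing the number of cases by the total number of births (stillbirths + live births").
- Size: "The prevalence of small-for-gestational-age will be calculated by dividing the number of cases by the total number of live births". Growth and developmental delay also use live births.
- Low birth weight: no denominator is given. Section 9.3.2.2.3.3 defines it for the infant: "An infant with low birth weight will be classified as weighing under 2500 g".
- Interval, for every primary and secondary outcome: "Prevalence of primary and secondary outcome measures will be presented with 95% CIs for binomial proportion".

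Neither the inclusion nor the exclusion criteria (sections 9.2.4.1 and 9.2.4.2) restrict plurality. Plurality is recorded at delivery (section 9.2.8, repeated in Appendix F): "Birth order (for multiple births), and number of fetuses".

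Section 9.2.4 mentions correlation once: "Any within-patient pregnancy correlations will be accommodated in the analysis as part of the statistical analysis plan (SAP"). The sentence before it is about women who contribute more than one pregnancy.

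Section 9.7.2.5.1 compares cohorts by a risk ratio and says that adjusted odds ratios may be explored. Its covariate list begins: "The covariates of interest may include the maternal age, prior history of elective or therapeutic pregnancy termination status, other migraine treatment exposures". Plurality of the current pregnancy is not named there, nor in the subgroup, sensitivity or stratified analyses (sections 9.7.2.1, 9.7.2.6, 9.7.2.6.1 and 9.7.2.6.2). Elsewhere, multiple births appear only as family reproductive history.

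**The concern.** A binomial interval assumes independent units. Co-twins are delivered at essentially one gestational age, so a preterm twin delivery adds two cases to the numerator and two births to the denominator but only about one independent piece of information. Twins are also more often preterm and light, so pairs carry a disproportionate share of the cases, which inflates the variance further. An analysis that followed section 9.7.2.4 literally would report intervals for a stated secondary objective that cover less often than 95%.

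The second issue is comparability. Plurality is a strong determinant of preterm birth and birth weight, and this is a non-randomized registry. If twin rates differed between cohorts, the planned crude risk ratio would carry that difference, and none of the covariates named for adjustment is plurality.

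**Working it through.** **Plan's own figure.** For 3% vs 6%, two-sided 0.05 and 80% power: [1.960·√(2·0.045·0.955) + 0.842·√(0.03·0.97 + 0.06·0.94)]² / 0.03² = 748.4, that is 749 live births per group. Then 749/(0.85·0.62) = 1421.3. Both stated numbers (section 9.5) reproduce, with each live birth taken as independent.

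**Assumed inputs.** The documents give no twin rate, twin preterm risk or within-pair correlation. I take twin pregnancies q = 2-5%, preterm risk p_s = 8-10% in singletons and p_t = 50-60% in twins, with co-twins fully concordant for preterm birth. All coverage figures use the normal approximation.

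**Preterm birth.** The risk per birth is p = [(1−q)p_s + 2q·p_t]/(1+q). The variance of (cases − p·births) per pregnancy is

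V = (1−q)[p_s(1−p)² + (1−p_s)p²] + 4q[p_t(1−p)² + (1−p_t)p²].

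The design effect is D = V/[(1+q)·p(1−p)], and coverage of the nominal 95% interval is 2Φ(1.96/√D) − 1.

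Example with q = 3%, p_s = 8%, p_t = 60%: p = (0.0776 + 0.0360)/1.03 = 0.1103; V = 0.0723 + 0.0576 = 0.1299; D = 0.1299/(1.03·0.1103·0.8897) = 1.285; coverage 91.6%. At 749 births the half-width should be 2.54 percentage points rather than 2.24.

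| Twin pregnancies | Twin share of infants, 2q/(1+q) | D (coverage) at 10% vs 50% | D (coverage) at 8% vs 60% |
|---|---|---|---|
| 2% | 3.9% | 1.152 (93.2%) | 1.213 (92.5%) |
| 3% | 5.8% | 1.211 (92.5%) | 1.285 (91.6%) |
| 5% | 9.5% | 1.305 (91.4%) | 1.390 (90.4%) |

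A correct interval is therefore √1.152 to √1.390 = 1.07 to 1.18 times as wide. The result depends on whether the twin rate is quoted per pregnancy or per infant. If twins were 3% of infants, D would be 1.12-1.17.

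A simulation with 8% vs 60% agrees: coverage was 92.6% with twins at 3% of infants and 91.4% at 6%. With no drug effect, the crude risk-ratio test rejected in 6.7% and 8.4% of replicates against a nominal 5%.

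**Other outcomes, same q.** When pairs are not fully concordant, the twin term in V becomes q[2p_t(1−p_t)(1+ρ) + 4(p_t−p)²], where ρ is the within-pair correlation.

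- Low birth weight, if counted per infant (6% vs 55%, ρ = 0.5): D = 1.19-1.32, coverage 92.8-91.2%.
- Small for gestational age (10% vs 20%, ρ = 0.3): D = 1.02-1.05, coverage 94.7-94.4%.
- Major malformations (3% regardless of plurality): D = 1 + 2qρ/(1+q). With ρ = 0.3, D = 1.01-1.03 and power at 749 per group stays at 79-80%. In the limiting case of complete concordance, D = 1.04-1.10 and power is 79-76%.

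**Imbalance, no drug effect.** With twins in 4% of exposed and 2% of comparator pregnancies, the preterm risk ratio is 0.1308/0.1157 = 1.13 (10% vs 50%) to 0.1200/0.1004 = 1.20 (8% vs 60%). At 3% vs 2% it is 1.07-1.10.

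**The case against.** The strongest reply is that this belongs to the SAP, which is not shown. Section 9.2.4 defers correlation to the SAP, the patient in that clause is the mother, and a variance clustered on her would handle repeat pregnancies and co-twins alike. That a clustered variance remains possible stands. But the protocol does more than stay silent: it names the denominators and the interval, and its correlation clause is tied to repeat pregnancies. An SAP that followed the text would use the binomial interval.

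A reader might infer that plurality is shut out of every analysis. The documents do not support that. The covariate list is permissive, section 9.7.2.1 ends its subgroups with a general category of other risk factors, and section 9.7.2.6.1 allows further subgroups. Plurality is unnamed, not excluded.

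A reader might also infer that a twin imbalance will read as a drug effect. Nothing in the documents indicates that twin rates differ. Both cohorts are women with migraine and, where feasible, come from the same centers (section 9.9.2). Even the ratio of 1.20 would have a binomial-based interval of about 0.90 to 1.60 at 749 births per group.

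Finally, it is tempting to say that all the size and growth intervals are materially too narrow. For size for gestational age the calculation shows very little loss, and for growth no figure is available.

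**Conclusion.** The point holds for preterm birth and, if it is counted per infant, low birth weight. As written, the plan gives intervals with true coverage of roughly 93-90%, assuming 2-5% twin pregnancies, preterm risks of 8-10% in singletons and 50-60% in twins, and concordant pairs; low birth weight is close to this under its own assumed risks. The loss is small for size for gestational age and negligible for the primary malformation comparison and its sample size. Distortion of the crude preterm risk ratio (about 1.13-1.20 at 4% vs 2% of pregnancies) is conditional on an imbalance that a non-randomized registry cannot rule out but that the documents do not show.

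A related gap is that section 9.7.2.4 divides total malformation prevalence by pregnancies and birth prevalence by births, without saying how an affected twin pair is counted.

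**What to change.** In sections 9.7.2.4 and 9.7.2.5.1:

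1. State the unit of analysis for each outcome, including a denominator for low birth weight and a counting rule for malformations in multiple pregnancies.
2. For infant-level outcomes, replace the binomial interval with one clustered on the mother, for example from a modified Poisson or log-binomial GEE, and use the same variance for the risk ratio. This also covers repeat pregnancies.
3. Add a singleton-only or plurality-adjusted analysis of preterm birth and low birth weight (optionally size for gestational age), and tabulate multiples separately by cohort so that any imbalance is visible.

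No new data are needed, since number of fetuses and birth order are already collected. The cost is slightly wider intervals and a little more analysis work. A singleton-only analysis leaves out the few percent of infants from multiple births; plurality adjustment keeps them.

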## **9.7.2.5 Comparative Analysis**

### **9.7.2.5.1 Internal Comparator Analysis**

Primary and secondary outcome frequencies in the erenumab-aooe exposed cohort will be compared with the internal comparator cohort using the risk ratio (95% CIs). Also, comparisons may be explored using ORs adjusted to relevant covariates as applicable, if a sufficient number of outcomes are available in the subgroups. The covariates of interest may include the maternal age, prior history of elective or therapeutic pregnancy termination status, other migraine treatment exposures (such as preventive migraine treatments other than erenumab-aooe), migraine type, and baseline alcohol status. In

addition, erenumab-aooe exposure specific covariates such as any preconception CGRP mAb exposure (> 5 half-lives prior to LMP) and cumulative duration of exposure to migraine therapies during pregnancy may be explored.

Additionally, to assess the impact of exposure on the primary outcomes the propensity score matching may be explored. Baseline characteristics such as age, migraine history (eg, type of migraine), migraine severity (eg, frequency, duration, treatment burden) and parameters of obstetric history will be explored to match between the erenumab-aooe exposed and internal comparator cohorts.

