Similar descriptive analyses summarized above will be performed on the internal comparator cohort consisting of pregnant women with migraine who were not exposed to erenumab-aooe. If sufficient numbers are observed, a subgroup analysis will be performed by exposure to other migraine preventive treatments (other than erenumab-aooe).

Outcome frequencies will be described with both the internal comparator cohort and other available background prevalence from external comparator cohort(s). The primary analysis will be adequately powered to detect an a priori clinically meaningful difference in the proportion of major congenital malformations between the erenumab-aooe exposed cohort and the internal unexposed cohort. The comparison of the erenumab-aooe exposed cohort to the internal comparator cohort will be performed using the risk ratio and 95% CIs.

In addition, comparisons may be explored using odds ratios (ORs) adjusted to relevant covariates as applicable, if sufficient number of outcomes are available in the subgroups. Sensitivity analysis for spontaneous abortion as occurring before 22 weeks of gestation, for congenital malformations excluding women with exposure to known or potential teratogenic medications during pregnancy, and other potential sensitivity analyses of interest (if sufficient numbers allow) will be performed.

Existing data from external comparator cohort(s) will be used to compare the prevalence of selected adverse pregnancy events and of selected adverse fetal, neonatal, and infant events at birth and through at least the first year of life of infants in the registry (where available). The MACDP will be the primary external comparator cohort. Reports from The European Surveillance of Congenital Anomalies (EUROCAT) will also be used for supportive evidence and comparisons of outcome prevalence, in addition to other possible external databases as they become available. These comparisons will be based on examinations of point estimates and 95% CIs from each of the sources, and no inductive statistical inferences will be made.

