## 7.2 Rationale

Congenital malformations, structural (eg, cleft lip/palate, heart defects, neural tube defects, heart defects, abnormal limbs) and functional/developmental (eg, sensory problems, metabolic disorders, nervous system problems, degenerative disorders), affect about 3.0 per 100 live births in the U.S. (CDC, 2008) and are the leading cause of infant deaths (about 20% of all infant deaths) (Matthews et al, 2015). The European Surveillance of Congenital Anomalies (EUROCAT) estimated the prevalence of congenital anomalies as 25.6 per 1,000 live births (95% confidence interval [CI] 25.4 to 25.8) from 2012 to 2016 (EUROCAT Website Database, 2018).

It is inconclusive whether pregnant women with migraines have shown an increased risk of adverse pregnancy and infant outcomes. When comparing 777 women suffering from migraine with 182 non-migrainous women in the United Kingdom, the incidence of miscarriage or stillbirth (27% versus 29%) and toxemia (both 18%) were very similar in both groups, and the overall incidence of birth defects were similar (3.36% versus 3.97%) (Wainscott et al, 1978).

Triptans are currently classified as a category C drug. Data from a prospective Pregnancy Registry observing birth defects in 4.2% (95% CI 2.6% to 6.5%) of infants born to women using Sumatriptan during pregnancy (Ephross and Sinclair, 2014), which is consistent with general population birth defect rates. Compared to a non-migraine cohort of German pregnant women, the rates of major birth defects (adjusted odds ratio [OR] 0.84), spontaneous abortions (OR 1.20), preterm delivery (OR 1.01), and preeclampsia (OR 1.33) were not increased in 432 triptan-exposed pregnancies (Spielmann et al, 2018).

In a meta-analysis of publications regarding pregnancy outcomes following prenatal exposure to triptans, no significant increases in pregnancy outcomes rates were observed when comparing the triptan-exposed group with the migraine (no triptans) control group (major congenital malformations, prematurity, or spontaneous abortions) and when comparing the triptan-exposed group with the healthy controls (major congenital malformations) (Marchenko et al, 2015). However, when compared with healthy controls, the triptan-exposed group and the migraine (no triptans) control group had increased rates of spontaneous abortions and major congenital malformations, respectively.

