#### **9.7.1.2 Primary Analysis**

The final primary analysis will be conducted once all data collection is complete, including up to 21 months of follow-up for enrolled patients. Annual reports for safety reporting requirements will be generated, with an interim analysis at 3 years.

The primary outcome for this study is the comparison between proportions of major congenital malformations in infants of women with migraine exposed to erenumab-aooe during pregnancy with the unexposed internal comparator. All other outcomes will be classified as secondary. Variables identified for the subgroup analysis will be evaluated as potential confounders in the primary comparative analysis of the risk ratio for major congenital malformations in the erenumab-aooe exposed and unexposed internal comparator.

Data analysis for major congenital malformations will be based on the first trimester exposure to erenumab-aooe. Adjudicated major congenital malformations reported up to 1 year of age by the mother or by an HCP will be included in the primary analysis. Women who have received any first trimester prenatal testing after enrollment, with either negative or positive test result will be included in the primary analysis, **except**:

- Women who have received first trimester prenatal screening, in which either aneuploid disorders or genetic disorders that cause major congenital malformations have been detected, because these disorders are unrelated to medication use
- Any prematurity-related disorders and transient conditions
- Women where the outcome is known, prior to enrollment in the registry, either positive or negative, for major congenital malformations that are unrelated to genetic or aneuploid disorders will be analyzed separately as a subgroup analysis.

In addition to the comparison to an unexposed internal comparator cohort, results will be descriptively compared to existing data sources or published reports representing the general population prevalence of birth defects in the general population (see [Section 9.2.1.1.1](#)). Additional external data sources for comparison will be considered as they become available during the study.

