### **9.9.3 Analysis Limitations**

Expected low enrollment may limit the ability to address multiple strata or subgroups due to low sample size. Adequately powered statistical comparisons to the internal comparator cohort of women with migraine who are unexposed to erenumab-aooe could also be impacted by low enrollment; adjustment for covariates may not be feasible. The comparison of the internal comparator cohort to erenumab-aooe-exposed women will be performed and adjusted to relevant covariates, if sufficient number of outcomes are available.

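### The internal comparison uses risk ratios, but the only covariate-adjusted measure named there is the odds ratio, so for common secondary outcomes crude and adjusted results would not be on the same scale

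*Protocol*

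**What the plan says.** Section 9.7.2.5.1 sets the measure for the internal comparison: "Primary and secondary outcome frequencies in the erenumab-aooe exposed cohort will be compared with the internal comparator cohort using the risk ratio (95% CIs"). The next sentence turns to covariates and changes the measure: "comparisons may be explored using ORs adjusted to relevant covariates as applicable", on condition that the subgroups yield enough outcomes. The Abstract says the same: "comparisons may be explored using odds ratios (ORs) adjusted to relevant covariates as applicable".

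Other sections mention adjustment of the internal comparison but settle no measure:

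- Section 9.7.1.2 says of the subgroup variables that they "will be evaluated as potential confounders in the primary comparative analysis of the risk ratio" for malformations. It names the risk ratio but no method for adjusting it.
- Section 9.7.2.6.1 would consider subgroup covariates for adjustment in the primary analysis, again without a measure.
- Section 9.9.3 says that the comparison "will be performed and adjusted to relevant covariates, if sufficient number of outcomes are available".
- Propensity score matching (9.7.2.5.1) is optional and tied to the primary outcome. Section 9.7.2.4 allows matching or stratification in general terms.
- The time-varying Cox model (9.7.2.6) is a sensitivity analysis.

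For secondary outcomes, the odds ratio is therefore the only covariate-adjusted measure named in the main internal comparison.

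**The concern.** The protocol wants to know how far confounding explains any difference. Section 9.9.1.3 expects women with more severe migraine to be channelled to erenumab, and says that baseline severity and prior treatment are recorded so that confounding by indication can be assessed. The usual way to judge this is to see how far the estimate moves on adjustment.

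If the crude estimate is a risk ratio and the adjusted one an odds ratio, part of the movement comes from the change of measure. For a rare outcome that part is negligible. For a common one, the adjusted figure can lie further from 1 than the crude figure although adjustment did nothing. It can also stay level although adjustment removed real confounding. At stake is how adjusted results for the common secondary outcomes are read. The primary comparison is hardly touched.

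**Working it through.** **Step 1. The plan's own figure.** Section 9.5 sizes the study on a risk ratio: 3% against 6%, 80% power, alpha 0.05, 1:1 allocation. Sidedness is not stated; two-sided is used here. With the pooled-variance formula for two proportions and no continuity correction:

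n = [1.960 × √(2 × 0.045 × 0.955) + 0.8416 × √(0.03 × 0.97 + 0.06 × 0.94)]² / 0.03² = (0.5746 + 0.2461)² / 0.0009 ≈ 748.4, so 749 live births per group.

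Enrolment: 749 / (0.85 × 0.62) = 1421. Both stated figures are reproduced, and all six rows of Table 4 agree to within 1. A one-sided test would give 590. The planning is thus on the risk-ratio scale throughout.

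**Step 2. Odds ratio implied by a risk ratio.** With comparator risk p0 and exposed risk p1 = RR × p0,

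OR = [p1/(1 − p1)] / [p0/(1 − p0)] = RR × (1 − p0)/(1 − p1).

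Inputs for p0:

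- 3%: the planning rate for major malformations (9.5).
- 10%: small-for-gestational-age, from the 10th-percentile definition (9.3.2.2.3.2); assumed to hold in the comparator.
- 18% and 27%: women with migraine in a cited UK study (7.2), where "the incidence of miscarriage or stillbirth (27% versus 29%) and toxemia (both 18%) were very similar in both groups". Illustration only.

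| p0 | OR at RR 1.5 | excess over RR | OR at RR 2.0 | excess over RR |
|---|---|---|---|---|
| 3% | 1.52 | 1.6% | 2.06 | 3.2% |
| 10% | 1.59 | 5.9% | 2.25 | 12.5% |
| 18% | 1.68 | 12.3% | 2.56 | 28.1% |
| 27% | 1.84 | 22.7% | 3.17 | 58.7% |

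Example at 10% and RR 1.5: (0.15/0.85)/(0.10/0.90) = 0.1765/0.1111 = 1.59. For a protective RR of 0.75 the odds ratio is 0.73, 0.71 and 0.69 at 10%, 18% and 27%, again further from 1. At RR = 1 the odds ratio is 1 at every p0.

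**Step 3. The masking direction.** Suppose the crude risk ratio is 1.50 and the adjusted odds ratio is also 1.50. At p0 = 10% the exposed odds are 1.5 × 0.1111 = 0.1667, so p1 = 0.1667/1.1667 = 0.143 and the risk ratio is 1.43. At p0 = 27%, p1 = 0.5548/1.5548 = 0.357 and the risk ratio is 1.32. A reader would see no change where the risk ratio had in fact fallen.

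**Step 4. Non-collapsibility.** An odds ratio can also move when the model includes a strong predictor that is no confounder. Take a binary covariate, split 50/50 and independent of exposure, with an assumed odds ratio of 3 to 5 for the outcome, and a marginal risk ratio of 1.5. The conditional odds ratio is then 1.53 at 3%, 1.61 to 1.63 at 10% (marginal 1.59), 1.73 to 1.78 at 18% (marginal 1.68), and 1.92 to 2.01 at 27% (marginal 1.84). None of this movement is confounding.

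**The case against.** Several stronger readings are tempting, and the documents do not support them.

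- *A reader might infer that odds ratios are the planned adjusted analysis.* The text makes them optional, exploratory and conditional on enough outcomes. The committed measure is the risk ratio (7.3, 9.7.2.5.1), and section 9.7.1.2 speaks of confounders of the risk ratio.
- *A reader might infer that the plan overstates effects.* An odds ratio is a valid measure. It misleads only when it is read as a risk ratio or set beside one. With no effect, the change of scale produces no signal.
- *A reader might infer that the primary result is affected.* At 3% the gap is 2-3%. Rare secondary outcomes such as stillbirth (about 8 per 1000 in the surveillance data cited in 9.2.1.1.1) are equally unaffected.
- *A reader might take 18% and 27% as this registry's rates.* They come from one cited study. Miscarriage and stillbirth are combined there but analysed separately here, and toxemia is not a registry endpoint. Section 9.9.1.3 expects early losses to be under-recorded. The 3.17 also needs an exposed risk of 54%.

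Sampling error is larger than the gap in the 10% case. With 749 live births per group and risks of 15% and 10%, the standard error of log RR is √(0.85/112.35 + 0.90/74.9) = 0.140, so the 95% interval around 1.5 is about 1.14 to 1.97. The choice of regression model could also reasonably be left to the statistical analysis plan.

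All of this stands, and it makes the point small. It does not remove it. The protocol itself names the adjusted measure, so the mismatch is not a detail left open, and the shift in scale is systematic where sampling error is not. Nothing prevents a crude odds ratio from being reported as well, but nothing calls for one.

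**Conclusion.** The point holds as a minor inconsistency of scale, confined to optional adjusted analyses of common secondary outcomes. The case closest to a registry endpoint is small-for-gestational-age. If the comparator rate is about 10%, risk ratios of 1.5 and 2.0 correspond to odds ratios of 1.59 and 2.25 without confounding, a gap of about 6% to 12.5%. The 18% and 27% cases show how the gap grows; they rest on background figures and do not predict this registry. The non-collapsibility figures rest on an assumed covariate.

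The consequence is one of interpretation: movement from a crude risk ratio to an adjusted odds ratio cannot be read as the effect of adjustment, although sections 9.7.1.2 and 9.9.1.3 intend such a reading of confounding. The primary objective, the power and the sample size are sound on this point.

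**What to change.** In section 9.7.2.5.1 and the Abstract, replace the adjusted odds ratios with adjusted risk ratios for primary and secondary outcomes alike. Modified Poisson regression (log link, robust variance) or standardization from a logistic model would serve. The robust variance can be clustered on the woman, which fits the repeat pregnancies that section 9.2.4 already leaves to the statistical analysis plan. Sections 9.7.1.2 and 9.9.3 should name the same measure.

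If odds ratios are kept, report the crude odds ratio beside each adjusted one. This removes the change of scale but leaves the smaller non-collapsibility shift (1.59 to 1.61-1.63 in the 10% example).

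The cost is a few words and standard SAS code. No further data are needed, and 749 live births and 1421 women per group are unchanged.
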